9.6.2 Laboratory Test Results

For screening purposes, chemistry, hematology, coagulation, and triglycerides will be analyzed by the local laboratory. For eligibility determination on day -3 to -1, only ALT, AST, and TBIL in the chemistry panel will be performed at the local laboratory. On-study laboratory assessments, unless specifically noted in contrary, will be assessed by a central laboratory.

Results from the laboratory will be included in the reporting of study for Hematology, Chemistry, Coagulation and Urinalysis. A list of laboratory assessments to be included in the outputs is included in the protocol.

Laboratory assessments will be summarized by treatment group and scheduled time points during the treatment period using descriptive statistics for each cohort. Change and percentage change from baseline over time, shift from baseline to maximum post baseline, and shift from baseline to minimum post baseline may also be provided if applicable.

9.6.3 Vital Signs

The summary statistics over time and/or changes and percentage changes from baseline over time for scheduled time points will be produced for the following parameters:

- Systolic Blood Pressure (mmHg)
- Diastolic Blood Pressure (mmHg)
- Heart Rate (beats/min)
- Temperature (°C or °F as per available data)

Subject level data listing will be reviewed.

9.6.4 Physical Measurements

Physical measurement data (I.e. Weight and BMI (kg/m²)) will be summarized descriptively at scheduled time points.

Subject level data listing will be reviewed.

9.6.5 Electrocardiogram

Each ECG will include following measurements: PR, QRS, QT, QTc, RR.

The following summary will be provided for cohorts 1 to 5 and Cohorts 8 and 9 only.

Summaries over time and change and percentage change from baseline over each scheduled time points (including time points with single and triplicate measurements) will be provided for each ECG parameter by treatment group and cohort.

Further subjects' maximum change from baseline in QTcF will be categorized in following categories and the number and percentage of subjects in each treatment group and cohort will be summarized. Unscheduled assessments will be included in the determination of the maximum change.

<=30 msec

>30-60 msec

>60 msec

Subjects' maximum post baseline values in QTcF will also be categorized in the following categories and the number and percentage of subjects in each treatment group and cohort will be summarized. Unscheduled assessments will be included in the determination of the maximum post baseline value.

<=450 msec

>450-480 msec

>480-500 msec

>500 msec

Subject level data listing will be reviewed.

9.6.6 Exposure to Investigational Product

Details of each AMG 890 administration **may** be listed and reviewed for every subject. In addition, a listing of the unique manufacturing lot numbers, and a listing of the subjects administered each manufacturing lot number will be provided.

9.6.7 Exposure to Concomitant Medication

The number and proportion of subjects receiving lipid regulating therapies of interest will be summarized by medication category and preferred term by treatment group and cohort as coded by the World Health Organization Drug (WHO Drug) dictionary.

9.7 Other Analyses

9.7.1 Analyses of Pharmacokinetic or Pharmacokinetic/Pharmacodynamic Endpoints

Pharmacokinetic Analysis

The pharmacokinetic analyses will be performed by the Clinical Pharmacology, Modeling & Simulation group (CPMS).

Serum samples will be analyzed for AMG 890 concentrations using a validated assay.

Individual concentration-time plots for AMG 890 will be presented for each subject as well as mean concentration-time plots for each cohort.

Descriptive statistics for PK concentration data will be provided at each time point for each cohort.

Pharmacokinetic parameters including but not limited to AUC_{last} , AUC_{inf} , C_{max} , and t_{max} will be estimated using non-compartmental methods. Actual dosing and sampling times will be used for calculation of PK parameters. Summary statistics will be generated for each PK parameter for each dose cohort using the PK analysis set.

Subject level data listing will be generated for both PK concentration and PK parameter data.

Pharmacodynamic Analysis

Descriptive statistics for absolute value, change and percentage change for plasma Lipoprotein(a) by cohort and at scheduled time points during the treatment period will be presented using PD analysis set.

Figures for absolute value, change and percent change in plasma Lipoprotein(a) t will be generated by cohort and at scheduled time points, including the treatment period and any values collecting during the follow-up period (where applicable).

Descriptive statistics for actual value and change and percentage change from baseline will be provided for total cholesterol, Cholesterol fractions (very-low density lipoprotein cholesterol [VLDL-C], low-density lipoprotein cholesterol [LDL-C], and high-density lipoprotein cholesterol [HDL-C], triglycerides, apolipoprotein A1 [ApoA1] and total apolipoprotein B [ApoB]) at each scheduled time points during the treatment period by treatment group and cohort using Safety analysis set.

Subject level data listing will be reviewed.

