#### **13.1.2.4 Covariates and Subgroups**

Baseline values may be used as a covariate in analyses. For any variable, unless otherwise defined, baseline is defined as the last assessment taken prior to the first administration of AMG 890 or placebo.

No subgroup analyses are planned.

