2.2 Hypotheses and/or Estimations

AMG 890 will be safe and well tolerated when administered SC as a single dose in subjects with elevated plasma Lp(a).

AMG 890 PK and/or PD data from this study will support the selection of dose and frequency of AMG 890 administration for future multi-dose trials.

3. Study Overview

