4.1 Planned Covariates

Not applicable

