4.2 Subgroups

No subgroup analysis is planned.

5. Definitions

Age at time of enrollment

Subject age in years at time of enrollment will be collected in the clinical database.

AUC_{last}

Area under the concentration-time curve from time zero to the last quantifiable concentration.

AUC_{inf}

Area under concentration-time curve from time 0 extrapolated to infinity.

Baseline

Baseline values for Lp(a) are defined as the mean of screening and day 1 predose. If for any reason only 1 value is available, then that value will be used as baseline.

For any other variable, unless otherwise specified, baseline is defined as the last assessment taken prior to administration of AMG 890 or placebo.

ECG Baseline value

Analysis of ECG is applicable to cohorts 1 to 5 and 8 and 9 only.

Baseline ECG for cohorts 1 to 5 is defined as the mean of the triplicate values measured on Day -1. Baseline ECG for cohorts 8 and 9 is defined as the mean of the 3 triplicate values measured at the Day -3 to -1 dosing pre check visit. If there are any missing values, the mean of the non-missing values will be taken as baseline.

Change from Baseline

Change from baseline is the arithmetic difference between post-baseline and baseline.

Enrollment Date

Enrollment date is defined as the date on which subject was enrolled in the study.

End of Study for the Overall Trial

Defined as when the last subject is assessed or receives an intervention for evaluation in the study i.e. last subject last visit, following any additional parts in the study (e.g. Follow-up period, long term follow-up) as applicable.

End of Study for Individual Subject

Defined as the last date recorded on the End of Study form for an individual subject.

End of Treatment Date

End of Treatment Date for cohort 1 and 2 is the date of Day 113 visit, for Cohort 3 to 7 is the date of Day 225 visit and for cohort 8 and 9 is the date of Day 365 visit.

Fridericia-corrected QT Interval (QTcF)

The Fridericia correction will be calculated from the investigator reported QT (msec) and RR interval (msec), as follows:

$$\text{QTcF} = \text{QT}/\text{RR}^{1/3}$$

Investigational Product

The term investigational product is used in reference to AMG 890 or placebo.

Percentage Change from Baseline

Percentage change from baseline is arithmetic difference between post baseline and baseline divided by baseline values times 100.

Randomization Date

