9.1 General Considerations

Descriptive statistics will be provided for selected demographics, adverse events, vital signs, ECG and selected laboratory measurements. Descriptive statistics on continuous measurements will include means, medians, standard deviations, and ranges, while categorical data will be summarized using frequency counts and percentages. Data will be presented and summarized by treatment group and cohort at each scheduled time point. Graphical summaries of the data may also be presented.

Data for subjects receiving placebo will be combined across cohorts 1 to 5 and separately across cohorts 6 to 9.

When data are summarized by time, the values recorded against the scheduled time points listed in the protocol will be used. When assessing minimum/maximum increases or decreases over the study, all assessments, including unscheduled assessments will be used. Unless stated otherwise in the statistical analysis plan, the data analysis will be conducted using subjects in the safety analysis set. For statistical analyses comparing change from baseline, only subjects with both baseline and at least one post-baseline assessment will be included.

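### The SAP plans no placebo-adjusted or covariate-adjusted Lp(a) estimate and no confidence intervals, although the data are meant to support dose and frequency selection; adding them is a cheap improvement

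*SAP*

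**What the plan says.** SAP 9.7.1 (Pharmacodynamic Analysis) provides for "Descriptive statistics for absolute value, change and percentage change for plasma Lipoprotein(a) by cohort and at scheduled time points", in the PD analysis set, with matching figures. SAP 9.1 says what descriptive means: "Descriptive statistics on continuous measurements will include means, medians, standard deviations, and ranges". It also gives the layout, "Data will be presented and summarized by treatment group and cohort at each scheduled time point", and the placebo rule, "Data for subjects receiving placebo will be combined across cohorts 1 to 5 and separately across cohorts 6 to 9".

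On covariates, Protocol 13.1.2.4 is permissive: "Baseline values may be used as a covariate in analyses". SAP 4.1 (Planned Covariates) reads "Not applicable". SAP section 5 sets the reference value: "Baseline values for Lp(a) are defined as the mean of screening and day 1 predose". SAP 9.5 marks efficacy analyses as not applicable.

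On purpose, SAP 2.2 says that "PK and/or PD data from this study will support the selection of dose and frequency" for future multi-dose trials. Protocol 5.5.1 adds that cohorts 8 and 9 are there to give fuller PK and Lp(a) data for phase 3 dose and regimen selection.

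Neither the SAP nor the visible text of Protocol section 13 contains a treatment difference, a model, a standard error or a confidence interval, for Lp(a) or for adverse event incidence.

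**The concern.** The trial randomises to placebo, and the plan does not use that comparison for estimation. It matters for Lp(a) because eligibility is set by cut-offs on screening Lp(a) (70 to 199 nmol/L in cohorts 1 to 5; 200 nmol/L or more in cohorts 6 to 9), and the screening value is also half of the Lp(a) baseline. In cohorts 6 to 9, selection above a floor tends to raise the baseline. Part of any later fall from baseline can then be regression to the mean. Placebo subjects in the same stratum pass through the same selection, so subtracting their change would remove this in expectation. The plan tabulates them but does not subtract.

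Precision is the second issue. Choosing a dose and a dosing interval means comparing doses where the response may be flattening, and late visits where Lp(a) is recovering and effects are smaller. Active groups have 6 or 9 subjects. Without intervals, a reader can take noise between cohorts for a dose difference, or take zero events in a small cohort as reassurance.

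**Working it through.** **The plan's own figures.** The only statistical figures in SAP 3.2 are chances of seeing at least one adverse event, 1 − (1 − p)^n:
- n = 6, p = 0.20: 1 − 0.8^6 = 73.8% (stated 74%).
- n = 10, p = 0.20: 1 − 0.8^10 = 89.3% (stated 89%).
- All active, p = 0.05: the number is blacked out. Table 1 sums to 60, and 1 − 0.95^60 = 95.4% (stated 95%).

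All three reproduce. None concerns Lp(a).

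**Group sizes (Table 1 and the schedules).** Active: 6 per cohort, 9 in cohorts 6 and 7. Placebo in cohorts 1 to 5: 5 × 2 = 10. Placebo in cohorts 6 to 9: 3 + 3 + 2 + 2 = 10. Cohorts 1 and 2 end treatment-period visits at day 113, so after that the lower stratum has placebo from cohorts 3 to 5 only: 3 × 2 = 6. Scheduled visits after day 225 exist only for cohorts 8 and 9: 2 + 2 = 4.

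**Unadjusted 95% half-width, active minus placebo**, in units of a common SD: t(0.975, nA + nP − 2) × √(1/nA + 1/nP).

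| Comparison | Half-width (SD) | SD 10 points | SD 20 points |
|---|---|---|---|
| 6 vs 10 | 1.11 | 11 | 22 |
| 9 vs 10 | 0.97 | 10 | 19 |
| 6 vs 6 (cohorts 3 to 5, after day 113) | 1.29 | 13 | 26 |
| 6 vs 4 (cohorts 8 and 9, after day 225) | 1.49 | 15 | 30 |

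The SD of percent change is an assumption, because the documents give none. The 6 vs 6 row also applies to a comparison of two active cohorts of 6.

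**What a model could add.** With a common residual variance across a stratum of 40 subjects (33 df in cohorts 1 to 5), the 6 vs 10 half-width is 1.05 SD if baseline and outcome are uncorrelated. It is 0.91 SD at a correlation of 0.5 and 0.75 SD at 0.7, multiplying by √(1 − ρ²). The correlation is also an assumption.

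**Against the predicted effects.** Protocol 5.5.1 predicts a maximum reduction of 39% at 3 mg and more than 80% at 75 mg. A half-width of 11 to 22 points hides neither. Above 80%, however, at most 100 − 80 = 20 points remain, and a between-dose half-width of 13 to 26 points is of that order. The true SD may be smaller near the ceiling. In monkeys, Protocol 5.2.1 reports no significant difference between 3 and 10 mg/kg.

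**Zero events.** The exact two-sided 95% upper bound for 0/n is 1 − 0.025^(1/n): 45.9% for 0/6 and 33.6% for 0/9.

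**The case against.** The strongest reply is that nothing here is a mistake. Safety is the primary objective, the sample size is practical, Protocol 13.5.1 plans descriptive statistics and the SAP follows it. That stands. It is also true that Protocol 13.1.2.4 only permits a baseline covariate, so SAP 4.1 contradicts nothing.

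A reader might go further and infer that dose selection rests on raw cohort means with no stated precision. The documents do not support that. SAP 2.2 says that PK and/or PD data will support selection, and no decision rule is given. The planned summaries include change from each subject's own baseline, medians, SDs and ranges. With known group sizes, an unadjusted interval follows by hand; a covariate-adjusted one does not. Pooled placebo at the same visits would let a reader see drift, and averaging screening with day 1 predose dampens regression to the mean. SAP 8.6 also allows transformations or non-parametric methods if needed, so arithmetic percent change is not the only scale open to the analyst. SAP 3.2 already implies a 26% chance (100 − 74) of missing an event of 20% incidence in a cohort.

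The remedy has limits as well. Pooled placebo is not a purely within-cohort randomised comparator, and cohort 9 has wider age, BMI and diabetes criteria. The response is already relative to baseline, so the gain from a baseline covariate is unproven. Some protocol text around 13.5.3 to 13.5.4 may be removed, although SAP 9.7.1 reads as complete.

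What remains is that the placebo contrast and its uncertainty are left for readers to assemble, and SAP 8.6 refers to assumptions of methods that the SAP never specifies for Lp(a).

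**Conclusion.** The gap holds in a limited form. No placebo-adjusted or covariate-adjusted Lp(a) estimate and no confidence interval is planned, in a study whose data are meant to inform dose and frequency. It is a worthwhile addition and not a defect that invalidates the plan. It does not threaten detection of the large predicted reductions. It matters most for telling higher doses apart and for late visits, where the reference group shrinks from 10 to 6 or 4 and the unadjusted half-width grows from 1.11 SD to 1.29 or 1.49 SD. The sizes in points rest on an assumed SD of 10 to 20 points, equal in both groups, and on full attendance at the Table 1 numbers.

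**What to change.** Keep every descriptive table. Add to SAP 9.7.1, separately for cohorts 1 to 5 and cohorts 6 to 9, a model of log(Lp(a)/baseline) at each scheduled visit with dose group and log baseline. Report geometric mean percent change against pooled placebo with a 95% confidence interval, labelled as estimation only. Amend SAP 4.1 to name baseline Lp(a) as the covariate. Specify that:
- each visit uses only placebo subjects whose cohort has that visit scheduled, with the number shown;
- values below quantification follow SAP 8.3, stating whether the laboratory rule (the limit itself) or the biomarker rule (half the limit) applies to Lp(a), with a sensitivity check, because log means are sensitive to this under strong suppression;
- the report notes that pooled placebo is not a purely within-cohort randomised comparator.

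In SAP 9.6.1, add exact 95% intervals beside treatment-emergent adverse event incidence.

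The cost is a few extra outputs from data already collected, with no tests and no alpha. The drawback is that the intervals will be visibly wide.

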9.7.2 Qualitative assessment of AMG 890 in Urine

Urine samples will be collected in some cohorts and AMG 890 concentrations in urine may be analyzed so that fractions of dose eliminated unchanged in urine may be determined, if sufficient data are available.

Summary statistics by treatment group and cohort will be presented if appropriate using Safety analysis set.

10. Changes from Protocol-specified Analyses

Protocol specifies the analysis of adverse events leading to withdrawal of IP however as this is single dose study, this will not be a meaningful analysis. As a result it has been removed from the planned analysis.

11. Literature Citations / References

Study Protocol dated **07 December 2021**

12. Appendices

Appendix A. Handling of Missing or Incomplete Dates for Adverse Events and Concomitant Medications

Imputation Rules for Partial or Missing Stop Dates:

If the month and year are present, impute the last day of the month.

If only the year is present, impute December 31 of that year.

If the stop date is entirely missing, assume the event or medication is ongoing. If a partial or complete stop date is present and the 'ongoing' or 'continuing' box is checked, then it will be assumed that the AE or concomitant medication stopped and the stop date will be imputed, if partial.

Imputation Rules for Partial or Missing Start Dates:

		Stop Date						
		Complete: yyyymmdd		Partial: yyyymm		Partial: yyyy		Missing
Start Date		<1 st Dose	≥1 st Dose	<1 st Dose yyyymm	≥1 st Dose yyyymm	<1 st Dose yyyy	≥1 st Dose yyyy	
Partial: yyyymm	Equal to 1 st Dose yyyymm	2	1	2	1	N/A	1	1
	Not equal to 1 st Dose yyyymm		2		2	2	2	2
Partial: yyyy	Equal to 1 st Dose yyyy	3	1	3	1	N/A	1	1
	Not equal to 1 st Dose yyyy		3		3	3	3	3
Missing		4	1	4	1	4	1	1

1 = Impute the date of first dose

2 = Impute the first of the month
3 = Impute January 1 of the year
4 = Impute January 1 of the stop year

Note: For subjects who were never treated (first dose date is missing), partial start dates will be set to the first day of the partial month.

Note: If the start date imputation leads to a start date that is after the stop date, then do not impute the start date.
